7.2.2 Date of Onset of Adverse Event

The onset date of each AE will be assigned the date recorded on the eCRF.

If the day part of the onset date is missing, then the onset date will be imputed as having occurred on the first day of the given month and year; however, when the first dose of IMP was taken in the same given month and year, then the onset date will be imputed as the day of the first dose of IMP.

If the month and day of the onset date are missing, then the onset date will be imputed as having occurred on the first month and first day of the given year; however, when the first dose of IMP was taken in the same given year, then the onset month and day parts will be imputed as the month and day of the first dose of IMP.

In the unlikely event that the onset date is fully missing, then the onset date will be set to the date of first dose of IMP.

If the imputed date is later than the reported stop date, the imputed date will be set equal to the stop date. This conservative scheme ensures that an AE with partial or complete onset date will be treated as a TEAE.

7.2.3 Intensity Rating

The Investigator classifies AEs into one of the following intensity categories: ‘Mild’, ‘Moderate’, and ‘Severe’ (see study protocol).

7.2.4 Relationship to Study Drug

The Investigator classifies AEs into one of the following categories with respect to IMP causality: ‘Certain’, ‘Probably related’, ‘Possibly related’, ‘Unlikely to be related’, ‘Unrelated’ or ‘Unassessable/Unclassifiable’ (see study protocol).

For analytic purposes, ‘Certain’, ‘Probably related’, and ‘Possibly related’ will be classified as “Related” AEs and ‘Unlikely to be related’, ‘Unrelated’ and ‘Unassessable/Unclassifiable’ as “Unrelated” AEs.

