10.11 Safety Endpoints

10.11.1 Adverse Events

Adverse events will be recorded throughout the study and at early termination. Adverse events and medical conditions will be coded using the Medical Dictionary for Regulatory Activities (MedDRA) coding dictionary. Treatment-emergent adverse events will be defined as those events, which are newly occurring or worsening from baseline. In all cases only treatment emergent adverse events will be summarized.

Treatment-emergent adverse events will be summarized by treatment group as the number and percentage of subjects having any treatment-emergent AE, having an AE in each body system, and having each individual AE. (*Note: In any given category [e.g., body system] a subject will only be counted once.*) Adverse events will further be categorized by severity, relationship to study drug, and action taken. Other information collected will be listed, as appropriate.

Any event starting more than 5 days after the final dose of study drug will be excluded from the above described tables and only listed, unless the event caused discontinuation from the study

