An **unexpected adverse event (UAE)** is any AE not yet identified in nature, severity, or frequency in the current Clinical Investigators' Brochure or in the clinical safety updates.

Clinical Laboratory Changes: It is the Investigator's responsibility to review the results of all laboratory tests as they become available. For each abnormal laboratory test result, the Investigator needs to ascertain if this is a clinically significant change from baseline for that individual subject. The Investigator may repeat the laboratory test or request additional tests to verify the results of the original laboratory tests. If a laboratory value is determined to be an abnormal change from baseline for that subject, this is considered an AE.

INTENSITY

AEs will be graded on a 3-point scale and reported as indicated on the Case Report Forms. The intensity of an AE is defined as follows:

- Mild: Discomfort noticed, but no disruption to daily activity
- **Moderate:** Discomfort sufficient to disrupt normal daily activity and/or requires symptomatic treatment
- Severe: Inability to work or perform normal daily activity and requires treatment

STUDY DRUG CAUSALITY

Relationship of an AE to treatment will be assessed as follows:

- **Certain:** The AE is **clearly** related to the investigational agent(s).
- **Probably Related:** The AE is likely related to the investigational agent(s).
- **Possibly Related:** The AE may be related to the investigational agent(s).
- **Unlikely to be Related:** The AE is doubtfully related to the investigational agent(s).
- **Unrelated:** The AE is **clearly** NOT related to the investigational agent(s).
- Unassessable/unclassifiable: The AE is cannot be judged because information is insufficient or contradictory.

BACKGROUND PAH DRUG CAUSALITY

Relationship of an AE to treatment will be assessed as follows:

- **Certain:** The AE is **clearly** related to the background PAH agent(s).
- **Probably Related:** The AE is likely related to the background PAH agent(s).
- **Possibly Related:** The AE may be related to the background PAH agent(s).
- Unlikely to be Related: The AE is doubtfully related to the background PAH agent(s).
- Unrelated: The AE is clearly NOT related to the background PAH agent(s).
- Unassessable/unclassifiable: The AE is cannot be judged because information is insufficient or contradictory.

ACTION TAKEN

Action taken for an AE to treatment will be assessed as follows:

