7.2.7 Summary of Treatment-Emergent Adverse Events

A summary of all TEAEs will present numbers and percentages of the following by treatment group:

- Subjects with at least one TEAE
- Subjects with at least one IMP-related TEAE
- Subjects with at least one TEAE related to PAH background medication
- Subjects with at least one serious TEAE

- Subjects with a TEAE leading to permanent discontinuation of IMP

7.2.8 **Subjects with a TEAE leading to dose modifications of IMP Summaries of Adverse Events**

TEAEs will be separately summarized by treatment group for the following:

- Total number of TEAEs, total number subjects with at least one TEAE
- TEAEs by severity
- TEAEs by relationship to IMP
- TEAEs by relationship to PAH background medication
- TEAEs by action taken with IMP
- TEAEs leading to study withdrawal

TEAEs will be presented in alphabetical order of SOC and by decreasing order of incidence of the preferred terms.

For these summaries, a subject having the same TEAE multiple times will only be counted once for the corresponding preferred term. Similarly, a subject who experienced multiple TEAEs within the same SOC will be counted only once for that SOC.

A subject experiencing the same TEAE multiple times or at multiple severities will only be counted once under that preferred term at the worst severity rating. Similarly, a subject who experiences the same TEAE multiple times or at multiple severities across multiple preferred terms within the same SOC will only be counted once for the worst severity rating within the SOC.

A subject experiencing the same TEAE multiple times or at multiple relationships to IMP will only be counted once for the worst relationship to IMP within a preferred term. Similarly, a subject who experiences the same TEAE multiple times or at multiple relationships to IMP across multiple preferred terms within the same SOC will only be counted once for the worst relationship to IMP within the SOC. The same procedure will be used for relationship to PAH background medication.

A subject experiencing the same TEAE multiple times or at multiple actions taken to IMP will only be counted once for the worst action taken with IMP within a preferred term. Similarly, a subject who experiences the same TEAE multiple times or at multiple actions taken to IMP across multiple preferred terms within the same SOC will only be counted once for the worst action taken to IMP within the SOC.

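### The SAP labels adverse events whose causality could not be judged as Unrelated, which can understate the related-TEAE counts relative to a conservative rule

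*SAP*

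**What the plan says.** Investigators rate each adverse event on a six-level causality scale, once for study drug and once for background PAH therapy (Protocol Appendix 7). SAP 7.2.4 reduces the study-drug scale to two levels. Certain, Probably and "Possibly related’ will be classified as “Related” AEs"; the other three ratings go the other way: "Unlikely to be related’, ‘Unrelated’ and ‘Unassessable/Unclassifiable’ as “Unrelated” AEs". The part at issue is the last of these three: "Unassessable/Unclassifiable’ as “Unrelated” AEs". SAP 7.2.5 applies the same grouping to background therapy.

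Protocol Appendix 7 keeps two of those pooled ratings well apart. Unrelated is a positive finding, worded for background therapy as "clearly NOT related to the background PAH agent(s" and in parallel terms for study drug. Unassessable/unclassifiable is the absence of a finding: "The AE is cannot be judged because information is insufficient or contradictory".

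The two-level grouping feeds the overall table in SAP 7.2.7, which includes "Subjects with at least one IMP-related TEAE" and a matching line for background medication. SAP 7.2.8 adds tables by relationship, in which a subject "will only be counted once for the worst relationship to IMP within a preferred term". Protocol 10.11.1 asks only that "Adverse events will further be categorized by severity, relationship to study drug, and action taken"; it states no pooling, so the grouping first appears in the SAP.

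**The concern.** A rating that means the investigator could not decide is relabelled as a decision that the drug was not involved. An event rated Unassessable for both study drug and background therapy would be reported as unrelated to either, which no investigator said.

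The SAP takes the opposite direction for another kind of uncertain adverse-event data. In 7.2.2, partial or missing onset dates are resolved so that the event counts as treatment-emergent, and the SAP itself calls this conservative. No reason is given for treating uncertain causality the other way.

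The rating could plausibly be used in this trial. Protocol 4.1.1 describes the combined use of two prostanoids as novel, and 6.2.1 has every study-drug dose taken with inhaled treprostinil. Protocol 7.12.8 lists headache, nausea, diarrhea, flushing and dizziness as common reactions to both products. Attribution to one agent or the other may often be hard. At stake is how faithfully the related-TEAE lines describe what investigators recorded.

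**Working it through.** The plan states no figure that depends on this rule, so there is nothing to reproduce. The check is a counting argument followed by an illustrative range.

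**Inputs**
- Related = Certain, Probably, Possibly (SAP 7.2.4).
- Unassessable/Unclassifiable is grouped with Unrelated (SAP 7.2.4 and 7.2.5).
- Planned size is 120 subjects per arm (SAP 4.1), used only for the range.
- Frequency of Unassessable ratings: not given in either document.

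**Within one arm.** Let R be the number of subjects with at least one TEAE rated Certain, Probably or Possibly related. Let U be the number with no such rating but at least one TEAE rated Unassessable.
- SAP count = R.
- Count with Unassessable treated as related = R + U.
- Since U ≥ 0, R ≤ R + U. The SAP count is never the higher of the two, and the gap is U.

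A subject with an Unassessable event who also has a Possible-or-stronger event is already in R, so U is smaller than the number of subjects with any Unassessable event whenever such subjects exist. For the same reason, a percentage of events cannot be converted into a change in this subject-level count.

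**Illustrative size (assumed, not from the documents)**

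| Assumed U, % of subjects | Calculation | Subjects omitted per arm | Percentage points |
|---|---|---|---|
| 0 | 0.00 × 120 | 0 | 0 |
| 1 | 0.01 × 120 = 1.2 | about 1 | 1 |
| 5 | 0.05 × 120 | 6 | 5 |
| 10 | 0.10 × 120 | 12 | 10 |

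**Between arms.** With n subjects in each arm, and E and P denoting esuberaprost and placebo, changing the rule moves the difference in related-TEAE proportions by (U_E − U_P)/n. Nothing in the documents fixes the sign of that quantity.

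**Which tables depend on the rule.** The two related-TEAE lines in 7.2.7 do. The by-relationship tables in 7.2.8 do if they use the two-level grouping. Total TEAEs, serious TEAEs, TEAEs leading to discontinuation or study withdrawal, and the severity tables do not use causality.

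**A gap alongside the rule.** The worst-relationship rule in 7.2.8 needs an ordering of the ratings, but the SAP gives no rank for Unassessable.

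**The case against.** Several points against the concern stand.

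- A reader might infer that the rule does understate drug-related events. The documents support only that it can. If no event is rated Unassessable, nothing changes.
- A reader might infer that the related-TEAE figure can only be biased downward. The inequality compares two counting rules; it does not compare the SAP count with the truth. Related already takes in Possibly Related, which Appendix 7 defines as an event that may be related, and this could push the figure up. The net direction against the true number is unknown.
- A reader might infer a bias in favour of esuberaprost. The rule applies to both arms, ratings are made under blinding (SAP 3.2.5), and the between-arm difference could move either way.
- The effect on safety oversight is limited. No event leaves the all-TEAE tables, serious events are reported whatever their causality (Protocol 7.12.7.2), the DSMB reviews unblinded data, and SAP 7 plans no formal inferential testing for routine safety analyses.
- A six-level table may already be intended. The wording of 7.2.8 fits either a six-level or a two-level table. The table mock-ups (SAP 1) and the data-conventions addendum (SAP 6.2) are separate documents not available here. The absence of a separate row is therefore not established, only that the SAP does not specify one.
- Counting an unjudgeable event as Related is also a forced choice. This is a fair criticism of reclassification alone, and it is why the separate row matters most. It does not justify the Unrelated label, which conflicts with the protocol's own definition of the rating.

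**Conclusion.** The point holds as a minor matter of descriptive safety reporting. SAP 7.2.4 and 7.2.5 classify as Unrelated a rating that the protocol defines as not judgeable. Relative to a conservative rule, this can lower the number of subjects with at least one IMP-related or background-related TEAE, and it can never raise it. The shortfall is U, which may be zero; the range of about 1 to 12 subjects per arm rests wholly on assumed values of 1% to 10% of 120. The conclusion covers the related counts within each arm. It does not extend to the true number of drug-related events, to the between-arm difference, or to alpha, power or the primary result.

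**What to change.** In SAP 7.2.4 and 7.2.5, remove Unassessable/Unclassifiable from the Unrelated group. Then:
- report it as its own row in the relationship tables, for study drug and for background therapy;
- count it with Related in the two-level summary of 7.2.7, or at least give that count as a labelled conservative sensitivity figure beside the main one;
- state where it ranks in the worst-relationship rule of 7.2.8.

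The data-conventions addendum that SAP 6.2 already plans before unblinding could carry the change. No new data are needed. The cost is a few lines of text, one extra table row, and slightly higher related counts in both arms if the rating was used.

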7.2.5 Relationship to Background Therapy

The Investigator classifies AEs into one of the following categories with respect to background PAH drug causality, including treprostinil inhaled: ‘Certain’, ‘Probably related’, ‘Possibly related’, ‘Unlikely to be related’, ‘Unrelated’ or ‘Unassessable/Unclassifiable’ (see study protocol).

For analytic purposes, ‘Certain’, ‘Probably related’, and ‘Possibly related’ will be classified as “Related” AEs and ‘Unlikely to be related’, ‘Unrelated’ and ‘Unassessable/Unclassifiable’ as “Unrelated” AEs.

7.2.6 Action Taken with Study Drug

For each AE, the investigator classifies the action taken with the IMP under one of the following: ‘IMP Dose Increased’, ‘IMP Dose Not Changed’, ‘IMP Dose Reduced’, ‘IMP Drug Temporarily Discontinued’, ‘IMP Withdrawn’, ‘Unknown’, or ‘Not applicable’ (see study protocol).

7.2.7 Summary of Treatment-Emergent Adverse Events

A summary of all TEAEs will present numbers and percentages of the following by treatment group:

- Subjects with at least one TEAE
- Subjects with at least one IMP-related TEAE
- Subjects with at least one TEAE related to PAH background medication
- Subjects with at least one serious TEAE

- Subjects with a TEAE leading to permanent discontinuation of IMP

7.2.8 **Subjects with a TEAE leading to dose modifications of IMP Summaries of Adverse Events**

TEAEs will be separately summarized by treatment group for the following:

- Total number of TEAEs, total number subjects with at least one TEAE
- TEAEs by severity
- TEAEs by relationship to IMP
- TEAEs by relationship to PAH background medication
- TEAEs by action taken with IMP
- TEAEs leading to study withdrawal

TEAEs will be presented in alphabetical order of SOC and by decreasing order of incidence of the preferred terms.

For these summaries, a subject having the same TEAE multiple times will only be counted once for the corresponding preferred term. Similarly, a subject who experienced multiple TEAEs within the same SOC will be counted only once for that SOC.

A subject experiencing the same TEAE multiple times or at multiple severities will only be counted once under that preferred term at the worst severity rating. Similarly, a subject who experiences the same TEAE multiple times or at multiple severities across multiple preferred terms within the same SOC will only be counted once for the worst severity rating within the SOC.

A subject experiencing the same TEAE multiple times or at multiple relationships to IMP will only be counted once for the worst relationship to IMP within a preferred term. Similarly, a subject who experiences the same TEAE multiple times or at multiple relationships to IMP across multiple preferred terms within the same SOC will only be counted once for the worst relationship to IMP within the SOC. The same procedure will be used for relationship to PAH background medication.

A subject experiencing the same TEAE multiple times or at multiple actions taken to IMP will only be counted once for the worst action taken with IMP within a preferred term. Similarly, a subject who experiences the same TEAE multiple times or at multiple actions taken to IMP across multiple preferred terms within the same SOC will only be counted once for the worst action taken to IMP within the SOC.

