Subjects will continue participation in the study until it is formally concluded by the Sponsor. Subjects are expected to remain on study drug throughout their participation in the study unless/until IV or SQ prostanoid therapy is added or in the event of lung transplantation. If a subject discontinues the study for any reason prior to the formal conclusion of the study by the Sponsor, the subject will be asked to return to the clinical for an End of Study (Early Termination) Visit. Vital status will be assessed for all randomized subjects at the formal conclusion of the study. For randomized subjects who terminate early, vital status will be assessed three months following discontinuation unless the formal conclusion of the study occurs within the three month time period.

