7 ANALYSIS OF SAFETY

The safety assessments will consist of extent of exposure, AEs including SAEs, laboratory evaluations, vital signs, and ECG findings.

All safety analyses will be based on the Safety Population. No formal inferential testing will be reported for routine safety analyses.

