7.1 Extent of Exposure

Exposure to study drug will be calculated as the date of last dose of IMP minus the date of the first dose of IMP plus 1. If the date of last dose of study drug was missing or unknown and the

last drug record had no return date, no assumption will be made for exact exposure. These analyses will include:

- Duration of exposure (in months)
- Number exposed by time (weekly to 3 months, 3-6 months, 6-12 months, 12-24 months, 24-36 months, ≥ 36 months)
- Number exposed by dose (15 μ g, 30 μ g) by time (weekly to 3 months, 3-6 months, 6-12 months, 12-24 months, 24-36 months, ≥ 36 months)
- Maintenance dose during the study (dose subject maintained on IMP after titration period)

Exploratory analyses may be conducted to assess IMP exposure within subgroups (see Sections 6.7.1 and 6.7.2). If appropriate, graphs will display the use of IMP over time.

Similar presentations will be made for inhaled treprostinil use during the study.

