7.2.1 Treatment-Emergent Adverse Events

A treatment-emergent adverse event (TEAE) is defined as any event not present prior to the initiation of the IMP or any event already present that worsens in either intensity or frequency following exposure to the IMP.

Only TEAEs occurring after IMP exposure will be summarized. Any AE starting prior to the first dose of IMP (i.e., during the screening period) will be excluded from the summary analyses.

The following notes the planned presentations of TEAEs. Other presentations for TEAEs may be produced to support the sponsor's review and analyses of events of special interest.

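### TEAE tables give counts and percentages with no person-time rate, although time on drug varies widely and may differ by arm

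*SAP*

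**What the plan says.** SAP 7.2.7 sets the overview: "A summary of all TEAEs will present numbers and percentages of the following by treatment group". SAP 7.2.8 adds "Total number of TEAEs, total number subjects with at least one TEAE" and breakdowns by severity, relationship and action taken, and 7.2.9 repeats these within subgroups. Protocol 10.11.1 plans the same measure: "Treatment-emergent adverse events will be summarized by treatment group as the number and percentage of subjects having any treatment-emergent AE". Neither document plans a rate per patient-year, a time-to-first-AE analysis or a fixed-window AE table. SAP 7.2.1 leaves room for more ("Other presentations for TEAEs may be produced") but does not say what.

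Exposure is tabulated separately in SAP 7.1, in bands "weekly to 3 months, 3-6 months, 6-12 months, 12-24 months, 24-36 months" and a last band of 36 months or more. It is not linked to the AE tables.

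On when drug stops, Protocol 2.1 says "Subjects are expected to remain on study drug throughout their participation in the study unless/until IV or SQ prostanoid therapy is added", or on lung transplantation. On when AE counting stops, Protocol 10.11.1 removes from the tables events that start more than 5 days after the final dose, unless they caused discontinuation from the study. SAP 7.2.1 gives no end to the treatment-emergent window.

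**The concern.** A crude percentage mixes the risk of an event with the length of time over which it could be seen. That does no harm when both arms are observed equally long. Here the trial runs to 113 clinical worsening events with staggered entry, and Protocol 4.3 accepts that treatment duration will vary between subjects. Some of the events that define worsening also take the subject off study drug. If one arm worsens less, as the sample-size section assumes for esuberaprost, that arm may stay on drug longer and collect more adverse events at the same underlying rate. If that arm instead loses more subjects to intolerance, its percentages fall and later harm can be hidden. The planned tables do not let a reader separate these explanations from a real difference in risk.

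**Working it through.** **Inputs from the documents.** One-year worsening is 45% on placebo and 25% on esuberaprost, accrual takes 1.5 years, and the study lasts 2.5 years (SAP 4.1). The constant hazards are −ln(0.55) = 0.598 and −ln(0.75) = 0.288 per year.

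**Check of those inputs.** The documents give no AE or exposure-by-arm figure, so the only figure to reproduce is the event target. The hazard ratio is 0.288/0.598 = 0.481. The Schoenfeld formula at two-sided 0.01 and 90% power gives 112 events, against 113 stated. With 113 events, power is 90.5% at 0.01 and 97.3% at 0.05, matching the stated 90% and 97%.

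**Assumptions (not in the documents).** The AE hazard *a* is constant and equal in both arms. A share *f* of worsening events ends drug, so the stopping hazard is *h* = *f* × worsening hazard. There is no other discontinuation at first. AEs are counted only on drug. Potential follow-up U is uniform on 1 to 2.5 years.

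**Formulas.**
- E[exp(−kU)] = (exp(−k) − exp(−2.5k)) / (1.5k)
- Mean time on drug = (1 − E[exp(−hU)]) / h
- Crude AE proportion = a/(a+h) × (1 − E[exp(−(a+h)U)])

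**Worked case: f = 1, a = 0.3.**
- Placebo: k = 0.898 and E = 0.224, so 0.3/0.898 × 0.776 = 25.9%.
- Esuberaprost: k = 0.588 and E = 0.369, so 0.3/0.588 × 0.631 = 32.2%.
- The difference is 6.3 points although the risks are equal.

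| Share of worsening events that ends drug | Mean years on drug, placebo vs esuberaprost | False excess in points at a = 0.1, 0.3, 0.6 |
|---|---|---|
| All | 1.07 vs 1.36 | 2.6, 6.3, 9.1 |
| Half | 1.35 vs 1.54 | 1.7, 4.0, 5.7 |
| A quarter | 1.53 vs 1.64 | 1.0, 2.3, 3.2 |
| None | 1.75 vs 1.75 | 0, 0, 0 |

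**Reversal.** Let half of the worsening events end drug and add an assumed extra stopping hazard of 0.2 per year on esuberaprost. At a = 0.3 the percentages become 31.9% placebo and 30.9% esuberaprost. With an extra 0.3 per year they are 31.9% and 28.8%.

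**Early-onset events.** Take an AE with 60% risk in both arms, all within the first 4 weeks, and let every worsening end drug. The crude percentages are 58.8% and 59.4%, so they are nearly unbiased.

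**Person-time rates for that same early AE.** First events per 100 patient-years at risk come to 132 on placebo and 106 on esuberaprost, a ratio of 0.80 although the risks are equal. The ratio is 0.88 if half of worsenings end drug and 0.94 if a quarter do. Neither measure suffices alone.

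**The case against.** A reader might infer that exposure is expected to be longer on esuberaprost, so that equal risk will show as a drug excess. The documents do not support this. Neither states such an expectation; it follows from the assumed worsening rates only if worsening ends study drug. Protocol 2.1 names parenteral prostanoid and lung transplantation as the stopping points. SAP 6.4.2 lets subjects stay to study close on or off drug, and SAP 6.12 says leaving after a primary endpoint was not required. Protocol 7.10.1 and 7.10.2, by contrast, run participation to a confirmed event. These passages need to be reconciled; until then the share of events that ends drug is unknown, and zero bias is within the range.

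The risk window is also open. SAP 1 says the SAP supersedes the protocol's statistical section, and its TEAE definition has no end. If AEs are counted throughout time on study, the gap shrinks as more subjects stay after stopping drug. This stands, and it is a reason to fix the window.

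It can also be said that safety is descriptive ("No formal inferential testing will be reported for routine safety analyses"), that exposure is tabulated, and that a 6.3-point gap lies inside a 95% half-width of about 11 to 12 points at 120 per arm. So calling the percentages uninterpretable would go too far. But the two columns will still be compared, separate exposure tables do not correct them, and bias from unequal exposure can affect many accruing AE terms at once. The optional extra presentations commit the sponsor to nothing.

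Finally, person-time rates assume a roughly constant hazard. The early-onset example shows that relying on them instead of percentages could create a false benefit. This objection stands in full.

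**Conclusion.** The gap is real: no planned AE display accounts for time at risk in a trial where time on drug varies widely and may differ by arm. If it does differ, crude percentages for AEs that accrue over time can mislead in either direction.

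At an AE hazard of 0.3 per year the false excess on esuberaprost runs from 0 to 6.3 points; over hazards of 0.1 to 0.6 it runs from 0 to 9.1. These figures rest on the plan's own worsening rates, on counting AEs only on drug, and on assumed AE hazards and stopping shares. They do not predict direction, because extra intolerance dropout on active would offset or reverse them. Early-onset events are little affected. The remedy supplements the percentages and does not replace them.

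**What to change.** In SAP 7.2.7 and 7.2.8:

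1. Keep n (%) as planned.
2. Add subjects with a first event per 100 patient-years at risk, with the rate difference and a descriptive 95% CI. Do this for any TEAE, serious, IMP-related, leading to discontinuation, and each preferred term at or above 5%.
3. Add an n (%) table for the first 12 weeks, where exposure is close to equal. Under the model above with every worsening ending drug, mean time on drug in that window, (1 − exp(−h × 12/52))/h × 52, is 11.2 weeks on placebo and 11.6 on esuberaprost.
4. State one end of the TEAE window that defines both the numerator and the time at risk, reconciling the 5-day rule in Protocol 10.11.1 with the open definition in SAP 7.2.1.
5. State that the three displays are read together.

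The cost is SAP wording and routine programming. First and last dose are recorded (SAP 6.8.2), as are AE onset dates (SAP 7.2.2). A rule is needed for missing last-dose dates, where SAP 7.1 makes no assumption about exposure. The downside is small: more tables, and rates that can mislead for early-onset events if read without the percentages.
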